9.7.1 Association between Pharmacokinetics and Baseline Characteristics

To evaluate differential pharmacokinetics of 744LA in participants by age, gender, race, ethnicity, weight, body mass index (BMI), and smoking status, we will use GEE regression model to account the correlations of the PK parameters following three injections in Cohort 1 or five injections in Cohort 2. The analysis will be performed separately for each cohort. The associations between the PK parameters and the predictors will be tested in univariate models (include one predictor in each model) and

in a multivariate model (include all predictors). Each model will be adjusted for sites (US vs. Non-US sites) by cohort.

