2.4 Schema

Cohort 1

W = Week

Cohort 2

The 110 participants in Cohort 1 and 90 participants in Cohort 2 were randomized to one of the two study arms with an active GSK 744 to placebo ratio of 3:1, stratified by gender and region (US and non US), as follows:

Cohort 1

Arm 1: 82 participants received daily oral 744 (30 mg tablets) for 4 weeks, followed by an one week washout period, to establish safety and tolerability, followed by intra-muscular (IM) gluteal injections of 800 mg of 744LA (administered as two sequential 400 mg gluteal injections) at three time points at 12 week intervals as: Week 5, Week 17, and Week 29.

Arm 2: 28 participants received daily oral matching placebo and IM injections of vehicle-matched placebo on the same schedule as Arm 1.

Cohort 2

Arm 1: Approximately 66 participants will receive daily oral 744 (30 mg tablets) for 4 weeks, followed by a one week washout period, to establish safety and tolerability, followed by intra-muscular (IM) gluteal injections of 600 mg of 744LA (administered as one 600 mg gluteal injection) at five time points at 4 and 8 week intervals as: Week 5, Week 9, Week 17, Week 25, and Week 33.

Arm 2: Approximately 22 participants will receive daily oral matching placebo and IM injections of vehicle-matched placebo on the same schedule as Arm 1.

All participants will receive HIV testing with pre- and post-test counseling, in addition to risk-reduction counseling and condoms and lubricant. All participants will be followed according to the Schedule of Evaluations and Procedures provided in HPTN077 protocol Appendices I-IV.

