3.2 Secondary Objectives and Endpoints

Secondary Objectives

- Evaluate the safety and tolerability of GSK1265744 (daily oral 744 + 744LA) for 76 weeks of follow-up after final injection (each cohort will be analyzed separately)
- Evaluate the safety and tolerability of oral 744 from Week 0 to Week 5

- Evaluate the pharmacokinetics of 744LA administered as 800 mg IM every 12 weeks for 52 weeks of follow-up after final injection
- Evaluate differential pharmacokinetics of 744LA in participants by age, gender, race, ethnicity, weight, body mass index (BMI), and smoking status
- Evaluate the acceptability of 744LA injections
- Evaluate the effect of 744LA on sexual risk behavior by change from enrollment for repeat assessments to during the study period
- Evaluate HIV incidence and antiretroviral drug resistance, if any participants acquire HIV infection during the study
- Evaluate the safety, tolerability and pharmacokinetics of 744LA in the subset of women who use a hormone-based contraceptive

Secondary Endpoints

- Proportion of participants who discontinue either oral or injectable study product for reasons of toxicity, tolerability, or acceptability prior to completion of the full oral and injectable phases
- Proportion of participants experiencing Grade 2 or higher clinical AEs and laboratory abnormalities during 52 weeks following final injection (safety) and any AE that leads to discontinuation (tolerability) during the aggregate oral and injectable phases
- Proportion of participants experiencing Grade 2 or higher clinical AEs and laboratory abnormalities (safety) and any AE that leads to discontinuation (tolerability) in the oral phase and washout period
- Plasma drug levels of GSK1265744 at designated time points after each injection of 744LA (by cohort only)
- Plasma drug levels of GSK1265744 at designated time points after each injection of 744LA stratified by age, gender, race, ethnicity, weight, BMI, and smoking status
- Proportion of participants willing to use an injectable agent such as the study product for HIV prevention in the future
- Change from enrolment of self-reported sexual behaviour (number of sexual partners, episodes of unprotected anal and/or vaginal intercourse) during the study period using a standardized assessment tool (in aggregate only)
- Number of incident HIV infections through the study period, including number with treatment emergent resistance

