11.3 Pharmacokinetic and Other Secondary Analyses

11.3.1 List of Tables

Table 21 Summary of pharmacokinetic parameters by injection

Table 22 Assess the time to steady state of the plasma drug concentration, C_{τ}

Table 23 Associations of sex at birth (or BMI) with pharmacokinetic parameters

Table 24 Change in sexual risk behavior (number of sexual partners) from baseline

Table 25 HIV incidences during the study

Table 26 Reported pregnancies by treatment arm and cohort

Table 27 The proportion of women experiencing any Grade 2 or higher AEs (a) prior to completion of the full oral phase and (b) prior to completion of the full injection phase --- among the women who use any injectable hormonal contraception (combined cohort)

Table 28 The proportion of the women who discontinue the study product for reasons of toxicity, tolerability, or acceptability (a) prior to completion of the full oral phase and (b) prior to completion of the full injection phase—among the women who use any injectable hormonal contraception

Table 29 Summary of pharmacokinetic parameters by injection and cohort —among the women who use any injectable hormonal contraception

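### The multivariable PK model in SAP 9.7.1 enters weight and BMI together, which makes both adjusted coefficients imprecise and hard to read as body-size effects

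*SAP*

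**What the plan says.** The secondary objective in SAP Section 3.2 is: "Evaluate differential pharmacokinetics of 744LA in participants by age, gender, race, ethnicity, weight, body mass index (BMI), and smoking status". Weight and BMI are named as separate factors.

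Section 9.7.1 carries the same list into GEE models for the PK parameters. Each association is first "tested in univariate models (include one predictor in each model) and" then tested "in a multivariate model (include all predictors"). It adds "Each model will be adjusted for sites (US vs. Non-US sites) by cohort", and "The analysis will be performed separately for each cohort".

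The Appendix (Derived Variables) computes BMI from weight and height. Nowhere does the SAP leave one of the two out of the joint model, put height in its place, or give a rule for collinear predictors.

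On output, Section 11.3.1 lists "Table 23 Associations of sex at birth (or BMI) with pharmacokinetic parameters". It does not say whether the one-predictor or the multivariable model supplies that table.

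**The concern.** BMI is weight divided by height squared. Once weight is in the model, BMI can vary only through height, so its coefficient is in effect a height effect with the sign reversed. The weight coefficient at fixed BMI is likewise a height effect. Neither says whether a heavier participant of the same sex, age and race has a different exposure.

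The two variables also overlap strongly, so each has a much larger standard error than it would have alone. Body size could matter for exposure while both adjusted coefficients are non-significant or opposite in sign. Gender is drawn in as well: weight and BMI together fix height, and height differs by sex. Table 23 is planned around sex and BMI, so both of its associations would be affected if it is filled from this model.

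**Working it through.** The SAP gives no correlation, variance inflation factor or power for this analysis, so there is no figure of its own to reproduce.

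**Inputs from the SAP**
- Predictors: age, gender, race, ethnicity, weight, BMI, smoking status, plus US/non-US site (Section 9.7.1).
- Participants on active drug, an upper limit for each model: 82 in Cohort 1 (Section 2.4: "Arm 1: 82 participants received daily oral 744 (30 mg tablets) for 4 weeks") and about 66 in Cohort 2.
- About 60% women (Section 4.1).

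**Assumed inputs (not in the SAP)**
- Mean height 162 cm in women and 175 cm in men, so the overall mean is 0.6 × 162 + 0.4 × 175 = 167.2 cm.
- Within-sex height SD 6 to 8 cm; BMI coefficient of variation (CV) 12% to 25%.
- BMI unrelated to height within sex; both variables continuous.

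**Step 1. Inflation for a given correlation.** If r is the weight–BMI correlation given the other covariates, the standard-error factor is 1/√(1 − r²).

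| r | Factor |
|---|---|
| 0.80 | 1.67 |
| 0.866 | 2.00 |
| 0.90 | 2.29 |
| 0.943 | 3.00 |
| 0.95 | 3.20 |

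A factor of 2 to 3 therefore needs r of about 0.87 to 0.94.

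**Step 2. Where r is likely to lie.** On the log scale, ln(weight) = ln(BMI) + 2 ln(height). With BMI and height independent within sex, the factor becomes approximately √(1 + (CV of BMI / (2 × CV of height))²).
- Height SD 7 cm: CV of height = 7/167.2 = 0.0419, doubled 0.0837. BMI CV 18% gives √(1 + 2.15²) = 2.37; BMI CV 22% gives √(1 + 2.63²) = 2.81.
- Low end, height SD 8 cm and BMI CV 12%: √(1 + (0.12/0.0957)²) = 1.60.
- High end, height SD 6 cm and BMI CV 25%: √(1 + (0.25/0.0718)²) = 3.62.

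**Step 3. Simulation with the full predictor set.** The factor is the standard error with both measures in the model divided by that with one.

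| Height SD | BMI CV 12% | 18% | 22% | 25% |
|---|---|---|---|---|
| 6 cm | 1.96 | 2.66 | 3.20 | 3.55 |
| 7 cm | 1.76 | 2.37 | 2.74 | 3.10 |
| 8 cm | 1.61 | 2.15 | 2.50 | 2.74 |

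These are for N = 82; N = 66 gives nearly the same. A BMI–height correlation of −0.1 lowers them slightly, to about 1.5 to 3.4 over the whole grid.

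**Step 4. Gender.** In the same setting, the gender standard error with both measures, divided by that with BMI alone, is about 1.43 at height SD 6 cm, 1.34 at 7 cm and 1.27 at 8 cm. It hardly depends on the BMI spread.

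**Step 5. Illustration of the consequence.** Take one outcome per participant, a true BMI effect of 0.3 to 0.4 residual SD per BMI SD, height SD 7 cm and BMI SD 5. Power for BMI falls from 76–93% to 20–30% at N = 82 once weight is added, and from 67–90% to 16–28% at N = 66. This is simpler than the planned GEE. The predictors are person-level variables, though, so the inflation carries over to first order.

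**The case against.** The strongest reply is that Section 9.7.1 also plans one-predictor models, adjusted for site, in which weight and BMI cannot disturb each other. The matching endpoint in Section 3.2 asks only for drug levels stratified by each factor. A reader might infer that the secondary objective goes unanswered; the SAP does not support that, because the one-predictor models still estimate each association. They leave body size confounded with gender, age and race, however, and removing that confounding is the purpose of the joint model.

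Second, collinearity does not bias the estimates, and a joint test of the pair would still show whether body size matters. Both statements are right, but no joint test is specified. It might also be said that only the weight and BMI rows suffer; Step 4 shows that gender is affected too.

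Third, the size rests on assumptions, including continuous entry, which the SAP does not state. Section 10.2.1 splits BMI at its median for injection site reactions. With both variables split at the median, the factor was 1.34 to 1.57 under further assumed spreads. This stands, and the figure has to carry that condition.

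Fourth, a reader might take the Appendix BMI formula literally, left to right. It then returns weight itself, and the joint model would be singular. That reading rests only on missing brackets in plain-text notation. It is a notation error to correct, not evidence on this point.

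Finally, Section 3.2 names weight in its own right, so simply dropping it from the adjusted analysis would not serve the objective.

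**Conclusion.** The point holds as a minor flaw in a stated analysis choice. Followed as written, the multivariable model gives weight and BMI coefficients that mainly reflect height. With continuous entry and the assumed spreads, their standard errors are about 2 to 3 times larger than with one measure (plausible range about 1.5 to 3.5). The gender standard error is about 1.3 to 1.45 times that with BMI alone. None of these factors is a figure from the SAP. The damage is loss of precision and of clear meaning in one secondary analysis.

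**What to change.** In Section 9.7.1, replace the instruction to include every predictor with two multivariable GEE models per cohort. Each contains age, gender, race, ethnicity, smoking status and site plus one body-size measure: BMI in the first and weight in place of BMI in the second. State that the BMI model feeds Table 23. Weight and BMI then each get an interpretable adjusted estimate, and the mutual inflation factor falls to 1.0. The cost is a wording change and one extra model per cohort; mutually adjusted weight and BMI coefficients are no longer produced.

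As a separate notation correction, add the missing brackets to the Appendix BMI formula and correct the height unit.

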9.8 Study Medication Satisfaction Questionnaire

The Study Medication Satisfaction Questionnaire (SMSQ) will also be used to assess subject tolerability and satisfaction to the study medication in this trial. The SMSQ is a modified version of the current HIV Treatment Satisfaction Questionnaire (HIVTSQ) that does not include questions pertaining to treatment but rather study medication. The SMSQ is a 12-item self-reported scale that measures overall satisfaction with medication, general satisfaction/clinical, satisfaction with lifestyle/ease, and each individual satisfaction. This study uses the SMSQs (status version) and the SMSQc (change version).

The SMSQs will be administered at the following time points: Week 6, Week 18, and Week 30 in Cohort 1 and Weeks 6, 10, 18, 26, and 34 in Cohort 2. The SMSQc will be administered at Week 18 in Cohort 1 and Week 10 in Cohort 2.

For each question the responses will be summarized by the proportion of participants reporting the response on the Likert scale out of all those that answered the question at visit by the treatment arm. An overall treatment satisfaction score will be calculated for each participant at each visit. To evaluate the participants' experience of the medication with injection comparing to the experience of medication with tablets during the first 4 weeks of the study, the score derived from SMSQc will be summarized by treatment arm and compared between the treatment arms using t-test and using the linear regression model to adjust for site effect (US sites vs. Non-US sites). To evaluate the participants' experience of the medication with injection, the scores derived from SMSQs will be summarized by treatment arm and visit and compared between the treatment arms over time using GEE model to account for the correlations of the scores over time and will be evaluated the changes over time within the treatment arms. The analyses will be done by Cohort and in aggregate.

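### The SMSQc is analysed to compare injections with tablets, but its only planned inference compares active with placebo and leaves the route contrast without a confidence interval or test

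*SAP*

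**What the plan says.** SAP Section 9.8 uses two versions of the Study Medication Satisfaction Questionnaire: a status version (SMSQs) and a change version (SMSQc).

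- **Purpose of the SMSQc analysis:** the target is described as "experience of the medication with injection comparing to the experience of medication with tablets during the first 4 weeks of the study".
- **Analysis for that purpose:** "the score derived from SMSQc will be summarized by treatment arm and compared between the treatment arms using t-test", and a linear regression adjusted for US versus non-US sites.
- **Timing of the SMSQc:** "The SMSQc will be administered at Week 18 in Cohort 1 and Week 10 in Cohort 2", so each participant gives one change score.
- **Timing of the SMSQs:** "The SMSQs will be administered at the following time points: Week 6, Week 18, and Week 30 in Cohort 1". In Cohort 2 it also starts at Week 6. For these status scores a GEE model compares the arms, and the plan "will be evaluated the changes over time within the treatment arms".
- **Item level:** responses to each question are tabulated as proportions by visit and arm.

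The analyses are run by cohort and in aggregate. Sections 2.3 and 2.4 give both arms four weeks of tablets and then injections. In Cohort 1, for example, "28 participants received daily oral matching placebo and IM injections of vehicle-matched placebo on the same schedule as Arm 1".

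**The concern.** The stated question is about route: how do injections compare with the tablets taken first? A change questionnaire answers this within each participant. The quantity of interest is therefore the mean change score in an arm relative to the value that means no change. The planned t-test and regression estimate something else, namely the difference in mean change between active and placebo.

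At stake is whether the analysis answers its own question. If both arms came to prefer the same route to the same degree, the one p-value attached to the injection-versus-tablet purpose would be null, and nothing prespecified would say how precisely the shared preference was estimated.

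**Working it through.** **1. What the planned test estimates.** Write the mean SMSQc score, centred at no change, as r + a in the active arm and r in the placebo arm. Here r is the change common to everyone who moves from tablets to injections, and a is any modification by active drug. The between-arm difference is (r + a) − r = a. The common part r, which is the stated target, drops out. Adjusting for US versus non-US sites does not bring it back.

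**2. Whether another part of the SAP supplies r.**

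- *SMSQs (Section 9.8).* The first injection is at Week 5 and the first SMSQs at Week 6. There is no tablet-phase status score, so within-arm change in the SMSQs compares injections with later injections.
- *Generic tests (Section 9.3).* The paired t-test and signed-rank test are for two time points, where required. The SMSQc is a single assessment, and Section 9.8 does not call on these tests.
- *Summary by arm (Section 9.8).* Under Section 9.3 this gives mean, median, SD, quartiles and range. It shows r descriptively, but no CI and no reference value are specified.
- *Section 11 lists.* None of Tables 1–29 or Figures 1–10 covers the SMSQ.

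**3. Illustrative size.** The SAP states no figure that could be reproduced here. The assumptions are mine: two-sided 5% level, SD of 1, zero meaning no change, the same true shift d in both arms, and all randomized participants responding. Arm sizes are from Section 2.4: 82 and 28 in Cohort 1, about 66 and 22 in Cohort 2, hence 148 and 50 in aggregate.

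Between-arm test: the noncentrality is (d − d)/√(1/n₁ + 1/n₂) = 0, so the rejection rate is the type I error for any d. Simulation with d = 0.5 and 20,000 runs gave 4.9% in each cohort and 4.8% in aggregate.

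One-sample test against no change: power = 1 − F(t*) + F(−t*), where F is the noncentral t distribution with n − 1 degrees of freedom and noncentrality d√n, and t* is the two-sided 5% critical value. For example, with n = 82 and d = 0.5 the noncentrality is 0.5 × √82 = 4.53 and the power is 0.994.

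| Group | n | d = 0.2 | d = 0.3 | d = 0.5 |
|---|---|---|---|---|
| Cohort 1 active | 82 | 0.432 | 0.766 | 0.994 |
| Cohort 1 placebo | 28 | 0.175 | 0.334 | 0.723 |
| Cohort 1 both arms | 110 | 0.547 | 0.877 | 0.999 |
| Cohort 2 active | 66 | 0.360 | 0.670 | 0.979 |
| Cohort 2 placebo | 22 | 0.146 | 0.269 | 0.609 |
| Cohort 2 both arms | 88 | 0.458 | 0.795 | 0.996 |
| Aggregate active | 148 | 0.676 | 0.952 | >0.99 |
| Aggregate placebo | 50 | 0.284 | 0.548 | 0.934 |

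Full response makes these upper bounds. If 20% of Cohort 1 gave no SMSQc, 82 × 0.8 ≈ 66 and 28 × 0.8 ≈ 22 would remain, and the Cohort 2 rows would apply.

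**The case against.** The strongest reply is that the route answer is already planned descriptively. The sentence that sets the t-test first calls for a summary by arm, and item-level proportions by arm are also planned. A CI follows by hand from the mean, SD and n. This stands, and it limits the point: what is missing is a prespecified reference value and an interval or test against it.

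A reader might infer that an equal preference in both arms would be reported as no difference between injections and tablets. The document does not support that. Under the plan such a result would appear as two similarly shifted arm summaries beside a null between-arm p-value, and nothing in Section 9.8 says that the p-value will be read as a test of route.

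A reader might also infer that the between-arm test is an error. It is not. In a double-blind placebo-controlled trial (Section 4.2), whether active drug alters the injection-versus-tablet rating is a valid, randomized question. The within-person contrast is the weaker design. It has no concurrent tablet control, and it relies on recall of tablets that ended at Week 4, about 18 − 4 = 14 weeks earlier in Cohort 1 and 10 − 4 = 6 in Cohort 2. These limits belong in the report, but they do not make the between-arm test an answer to the route question.

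Finally, the outcome is minor. Section 3 names no satisfaction endpoint, the acceptability endpoint in Section 3.2 is willingness to use an injectable in future, and Section 10.1.1 lists only questionnaire completion. This stands too.

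**Conclusion.** The mismatch is real and modest. Section 9.8 states a route question and attaches to it only inference about active versus placebo. A preference common to both arms cannot be detected by that inference, whatever its size, and no other planned analysis gives an interval or test for it. A shared shift would still be visible in the arm summaries.

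That the common effect cancels follows from the design alone. The power figures are illustrative and depend on assumed shifts of 0.2 to 0.5 SD, full response, and a no-change value inferred from the questionnaire being a change version, since the SAP does not give its scoring. At the smaller shifts even the active-arm test would often miss, so the interval is more useful than the p-value. No primary or listed secondary conclusion is affected.

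**What to change.** In Section 9.8:

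- State how the SMSQc score is derived and which value means no change.
- For the injection-versus-tablet question, report the mean SMSQc score with 95% CI against that value, with a one-sample t-test or signed-rank test. Do this by arm and with both arms together, by cohort and in aggregate.
- Keep the between-arm t-test and the site-adjusted regression, labelled as addressing whether active drug modifies the change.
- Note that the within-person contrast has no concurrent tablet control and relies on recall over a period that differs by cohort.

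The cost is a few sentences and one table column. No new data are needed and the primary analysis is untouched. The downside is one more estimate for a minor outcome that is not in the Section 11 lists.

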9.9 Acceptability Questionnaire

Baseline acceptability questionnaire (BAQ) will be administered at baseline Week 0 visit in both cohorts. Follow-up acceptability questionnaire (FAQ) will be administered at Weeks 6, 18, and 30 in Cohort 1; at Weeks 6, 10, 18, 26, and 34 in Cohort 2.

The scores will be derived from the items in BAQ/FAQ at each visit and then will be compared between the treatment arms. The scores derived from BAQ will be summarized and compared between the treatment arms using t-test and using the linear regression model to adjust for site effect (US sites vs. Non-US sites). The scores derived from FAQ will be summarized and compared between the treatment arms using GEE model to account for the correlations of the scores over time and will be evaluated the changes over time within the treatment arms. The data will be analyzed by cohort and in aggregate.

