4.7 Randomization

Enrolled participants are randomized to one of two study arms with an active GSK1265744 to placebo ratio of 3:1 in two cohorts. The arm randomization is stratified by

gender and region (US and non-US sites) and done in blocks to ensure balanced treatment assignments within each gender and region (US and non-US). The randomization scheme is generated, operationalized and maintained by HPTN SDMC using Frontier Science & Technology Research Foundation, Inc. (FSTRF) system. Additional details regarding the process of randomization are included in the SSP Manual.

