7.2 Baseline Definition

The data collected at the enrolment date will be considered as the baseline data for monitoring and evaluating the safety, tolerability, and acceptability of the investigating study product and other analyses unless it is specified. In some cases, the assessments at Week 5 prior to the first injection will be considered as the baseline.

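### The follow-up acceptability model names no baseline covariate, although acceptability is measured at Week 0; adding it is a free, low-severity gain in precision

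*SAP*

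**What the plan says.** Section 9.9 of the SAP sets the timing: "Baseline acceptability questionnaire (BAQ) will be administered at baseline Week 0 visit in both cohorts". For the follow-up instrument, where the second list of weeks belongs to Cohort 2: "Follow-up acceptability questionnaire (FAQ) will be administered at Weeks 6, 18, and 30 in Cohort 1; at Weeks 6, 10, 18, 26, and 34". By the visit schedule in Section 4.4 the first injection is at Week 5, so every FAQ assessment comes after an injection. Section 7.2 fixes the reference point: "The data collected at the enrolment date will be considered as the baseline data".

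Scoring is described jointly: "The scores will be derived from the items in BAQ/FAQ at each visit". The analyses then part. For baseline, "The scores derived from BAQ will be summarized and compared between the treatment arms using t-test", with a linear regression adjusted for US or non-US site as a second analysis. For follow-up, "The scores derived from FAQ will be summarized and compared between the treatment arms using GEE model to account for the correlations", together with changes over time within arms. Both are planned by cohort and in aggregate.

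No covariate is named for the follow-up model. No other section supplies one: Section 8.2.2 defines how a change from baseline is calculated where such a change is to be evaluated, and Section 9.9 does not call for a change from the BAQ.

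**The concern.** A measurement taken at Week 0 in randomised arms cannot show an effect of the study product. Testing it between arms asks only whether chance produced a difference, and with 28 placebo participants in Cohort 1 and about 22 in Cohort 2, a non-significant result would not establish balance.

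The comparison that can show an effect is the FAQ contrast. The FAQ series has no pre-treatment point of its own, so the BAQ is the only pre-treatment measure of acceptability, and Section 9.9 gives it no role there. Site adjustment is likewise written for the BAQ regression and not for the FAQ model. Other GEE analyses in the SAP do name covariates: site in Section 9.7.1; treatment, time, age and race/ethnicity in Section 9.10.

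At stake is the precision of a secondary comparison with small placebo groups. Leaving the covariates open also allows a choice between adjusted and unadjusted results after unblinding.

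**Working it through.** The SAP gives no sample size, power, SD or effect size for acceptability, so it has no figure to reproduce. The check is in SD units of the score.

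**Inputs from the SAP.** Section 4.7 gives an "active GSK1265744 to placebo ratio of 3:1 in two cohorts". Section 2.4 gives the arm sizes: for Cohort 1, "Arm 1: 82 participants received daily oral 744", with 28 on placebo; for Cohort 2, about 66 and 22. The aggregate is 82 + 66 = 148 against 28 + 22 = 50. FAQ visits number 3 in Cohort 1 and 5 in Cohort 2.

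**Assumptions not in the SAP.** BAQ-FAQ correlation r from 0.2 to 0.6; correlation s between FAQ visits of 0.5; two-sided 5% test; no loss of participants before the FAQ.

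**Step 1: size of the chance baseline imbalance.** SE = sqrt(1/n_active + 1/n_placebo).

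- Cohort 1: sqrt(1/82 + 1/28) = 0.219 SD
- Cohort 2: sqrt(1/66 + 1/22) = 0.246 SD
- Aggregate: sqrt(1/148 + 1/50) = 0.164 SD

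The probability of an imbalance above 0.2 SD in either direction is 36%, 42% and 22% respectively.

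**Step 2: gain from adjustment at one visit.** Adjusted variance = (1 - r²) × unadjusted variance. The unadjusted SE at one visit equals the Step 1 value.

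| r | Variance cut | Cohort 1 SE, unadjusted 0.219 |
|---|---|---|
| 0.2 | 4% | 0.214 |
| 0.3 | 9% | 0.209 |
| 0.5 | 25% | 0.190 |
| 0.6 | 36% | 0.219 × 0.8 = 0.175 |

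The difference detectable with 80% power is 2.80 × SE. At r = 0.5 it falls from 0.61 to 0.53 SD in Cohort 1, from 0.69 to 0.60 SD in Cohort 2, and from 0.46 to 0.40 SD in aggregate.

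**Step 3: precision and imbalance are one quantity.** Given an observed imbalance d, the unadjusted contrast is shifted by r × d. In Cohort 1 at r = 0.5 this shift has SD 0.5 × 0.219 = 0.11, hence variance 0.012. The saving in Step 2 is 25% of 0.219² = 0.25 × 0.048 = 0.012. The two are identical and must not be added.

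**Step 4: repeated visits.** For the mean of m visits, unadjusted variance is proportional to (1 + (m - 1)s)/m, and adjustment subtracts r². With m = 3 and s = r = 0.5 this is 0.667 against 0.417, a cut of 37.5%. With r = 0.3 it is 0.667 against 0.577, a cut of 13.5%. These figures rest on a second assumed correlation.

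**Step 5: simulation.** 20,000 trials of 82 against 28, three visits, all correlations 0.5, no true effect. The mean contrast was -0.002 SD unadjusted and -0.001 SD adjusted, so neither is biased. The SD of the estimate was 0.179 unadjusted and 0.143 adjusted. In trials with a baseline imbalance near 0.3 SD, the mean contrast was 0.144 SD unadjusted (0.5 × 0.3 = 0.15 expected) and -0.005 SD adjusted.

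**The case against.** The strongest reply is that nothing here is invalid. Under randomisation a GEE comparison without a baseline term is a sound analysis, and Step 5 confirms it. A reader might infer that chance imbalance biases the comparison or passes whole into the FAQ difference. Neither holds: the estimate is unbiased over repeated randomisations, and only r times the imbalance carries over.

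A reader might also infer that the SAP has decided to exclude baseline. It has not. Section 9.9 names no covariate at all for the FAQ model, so the fault is one of specification.

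The size is uncertain. The SAP shows no items, scoring rule or correlation for the two questionnaires. Answers given before any injection may predict later ones poorly, and at r of 0.2 to 0.3 the single-visit gain is only 4% to 9%. The planned aggregate analysis is also less exposed to imbalance than either cohort alone.

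Little depends on the contrast. The acceptability endpoint in Section 3.2 is a proportion willing to use an injectable in future, and Section 11 lists no table or figure of BAQ or FAQ scores. The BAQ test fits the general plan in Sections 9.3 and 9.4 to compare baseline characteristics between arms, and it is not presented as a treatment effect.

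All of this stands, and it keeps the severity low. It does not show that the model as written is as good as one with the BAQ score, which is already collected and costs nothing to include.

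**Conclusion.** The point holds as a low-severity free improvement to a secondary analysis. Section 9.9 spends the Week 0 score on a test that can reflect only chance and does not specify it where it could help.

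The unadjusted comparison is valid but less precise than it need be. The single-visit variance saving is 4% to 36% for r from 0.2 to 0.6, small at the lower end and material from about 0.5. It depends on a correlation that the SAP does not give and on no loss of participants before the FAQ. Fewer participants would raise the standard errors but leave these percentages unchanged.

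It would be wrong to conclude that the planned analysis is biased, that precision and imbalance are separate losses, or that the primary safety and tolerability conclusions are touched.

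**What to change.** In Section 9.9, prespecify the Week 0 BAQ score as a covariate in the FAQ GEE model, by cohort and in aggregate. If the two instruments do not share a score, enter the BAQ score as a prognostic covariate; it need not be on the same scale, and no change score is required. Add site (US or non-US) to the same model, as already done for the BAQ regression.

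Report the BAQ by arm descriptively and drop its between-arm test.

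The cost is two terms in a model already planned and one sentence in the SAP. No new data are needed.
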